10.3.2 Clinical Laboratory Tests

Laboratory data will be summarized by type of laboratory test. Descriptive statistics will be calculated for each laboratory analyte at baseline and at each scheduled time point. Changes from baseline results will be presented in pre- versus post-treatment crosstabulations (with classes for below, within, and above normal ranges). A listing of participants with Grade 2 or higher abnormal laboratory results based on FDA Guidance (FDA 2007) will be provided.

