AEs from single oral doses of SPH3127 from 25 to 800 mg were mild in severity and self-limiting. AEs were hypotension, dizziness, and neutropenia, among which hypotension and dizziness of the subjects may be related to the pharmacologic mechanism of action of SPH3127. Dizziness, likely as a consequence of hypotension, occurred only at the higher doses of SPH3127. Similarly, oral doses of 100 – 400 mg SPH3127 daily for 7 days produced AEs of mild, reversible hypotension, neutropenia, and ALT increases. No SPH3127-related AEs were observed following oral doses of 200 mg in a fed or fasted state in a crossover biopharmaceutics study. SPH3127 (50 - 200mg) was well-tolerated in a study of daily oral administration for 8 weeks to patients with mild-to-moderate hypertension. There were 2 serious adverse events (adenomyosis, infiltrating ductal breast cancer) in a single patient that were unrelated to treatment in the Phase 2 trial. There were also 5 significant adverse events in the Phase 2 trial, including: triglyceride elevation in a placebo patient; a moderate increase in liver function tests (ALT, AST, γ -GT) that resolved without sequelae on study drug discontinuation; a moderate elevation of AST in a patient who was not discontinued, but lost to follow-up; and, 2 patients with an exacerbation of hypertension, one of whom was discontinued from treatment. Although generally mild and transient, as a group across studies, elevations in liver function tests (e.g., ALT, AST, γ GT, ALP, DBIL, TBIL) showed an increase in frequency compared to placebo; these liver function test elevations do not appear to be dose-related.

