5.4 Exclusion Criteria

An eligible subject will not be enrolled in the trial if any of the following exclusion criteria are met:

- 1. Diagnosis of severe UC, defined as the presence of ≥ 6 bloody stools daily with one or more of the following: (1) oral temperature > 37.8°C or > 100.0°F; (2) pulse > 90 beats/min; (3) hemoglobin concentration < 10.5 g/dL; or erythrocyte sedimentation ratio (ESR) > 30.
- 2. Patients treated with oral mesalamine >2.4 g/d, systemic steroids or rectal steroids within 4 weeks prior to randomization, rectal mesalamine (within 2 weeks), immunomodulators or immunosuppressant drugs, including, but not limited to, IL-6 inhibitors, TNF inhibitors, anti-IL-1 agents and JAK inhibitors within 5 half-lives prior to randomization, antibiotics, anti-diarrheals (within 2 weeks), drugs blocking the renin-angiotensin system (e.g., direct renin inhibitors, angiotensin converting enzyme inhibitors, or angiotensin II receptor blockers) (within 4 weeks) or

administration of any investigational drug (within 4 weeks). Because SPH3127 is a direct renin inhibitor with the potential to reduce blood pressure, other classes of antihypertensives (e.g., calcium channel blockers, beta blockers, direct vasodilators, alpha blockers, central α2 antagonists) (within 4 weeks) will also be excluded. Drugs, herbal medicines and substances that inhibit or induce CYP3A4 (e.g., ritonavir, itraconazole, grapefruit juice) (within 2 weeks or 5 half-lives, whichever is longer) will be excluded.

- 3. History of colectomy or partial colectomy, colorectal dysplasia, Crohn's disease, toxic megacolon, or bleeding disorders.
- 4. A stool sample positive for enteric pathogens, including *Clostridium difficile*.
- 5. Patients with an estimated glomerular filtration rate (eGFR) \leq 60.
- 6. Patients with hepatic impairment or history of liver cirrhosis.
- 7. Serum creatinine > 1.5 times the upper limit of normal, aspartate aminotransferase (AST), alanine aminotransferase (ALT), total bilirubin (TBIL) or alkaline phosphatase (ALP) > 2 times the upper limit of normal.
- 8. Serious underlying disease other than UC.
- 9. Previous participation in clinical trials with SPH3127
- 10. Known hypersensitivity to tablet ingredients or history of a significant allergic reaction to any drug as determined by the investigator.
- 11. Known seropositivity or positive test at screening for an active viral/bacterial infection with:

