10.3.4 Vital Signs

Descriptive statistics of temperature, pulse/heart rate, and blood pressure (systolic and diastolic) values and changes from baseline will be summarized at each scheduled time

point. The percentage of participants with values beyond clinically important limits will be reported.

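### The only change-from-baseline display for laboratory tests has three normal-range classes, so it cannot show the size of a liver-test rise and records a further rise in a patient who enters above normal as no shift

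*Combined protocol and SAP*

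**What the plan says.** Section 10.3.2 plans three things for laboratory data.

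- By-visit summaries: "Descriptive statistics will be calculated for each laboratory analyte at baseline and at each scheduled time point". Section 10.1 defines these as n, mean, median, SD, minimum and maximum.
- Change from baseline: "Changes from baseline results will be presented in pre- versus post-treatment crosstabulations (with classes for below, within, and above normal ranges").
- A listing: "A listing of participants with Grade 2 or higher abnormal laboratory results based on FDA Guidance (FDA 2007) will be provided".

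On entry, exclusion 7 in Section 5.4 removes patients with "aspartate aminotransferase (AST), alanine aminotransferase (ALT), total bilirubin (TBIL) or alkaline phosphatase (ALP) > 2 times the upper limit of normal". Values above 1 and up to 2 times ULN are therefore admissible. Gamma-GT is in the Section 7.6 panel but not in exclusion 7. Exclusion 6, "Patients with hepatic impairment or history of liver cirrhosis", carries no laboratory threshold.

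Section 1.3.1 says of earlier studies that liver-test elevations, generally mild and transient, "showed an increase in frequency compared to placebo; these liver function test elevations do not appear to be dose-related".

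**The concern.** Safety and tolerability is the primary objective (Section 2.1), and Section 1.3.1 already names liver tests as a signal. The one table meant to show change has a single class for everything above normal. This has two consequences. A patient who enters above ULN cannot register an upward shift, however large the rise. For every other patient, a trivial crossing of the limit and a large elevation look the same.

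There is also a gap in timing. Section 10.3.2 does not say whether the post-treatment value is the last one, the worst one or one per visit. Section 7.6 schedules laboratory tests on Days 14, 28 and 56. If the last value is used, a rise at Day 14 or 28 that has resolved by Day 56 does not appear in the table.

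The plan treats its other safety measures more fully. For vital signs, "values and changes from baseline will be summarized at each scheduled time" point, together with the percentage beyond clinically important limits (Section 10.3.4). For QTc, Section 10.3.3 gives percentages above three absolute thresholds and two thresholds for increase. Laboratory tests get neither kind of summary.

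**Working it through.** The plan states no figure on this point, so there is none to reproduce. The check applies the planned classes to example values and then sizes the group affected.

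**Step 1: classification.** Take a value up to 1 times ULN as within normal and a value above it as above normal. Fold change is the post-baseline value divided by baseline. The values are illustrative.

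| Baseline (x ULN) | Post-baseline (x ULN) | Fold change | Cell in the planned table |
|---|---|---|---|
| 0.8 | 1.1 | 1.1/0.8 = 1.38 | within to above: shift |
| 0.8 | 10.0 | 10/0.8 = 12.5 | within to above: same cell |
| 1.2 | 5.0 | 5/1.2 = 4.17 | above to above: no shift |
| 1.5 | 8.0 | 8/1.5 = 5.33 | above to above: no shift |
| 2.0 | 3.0 | 3/2 = 1.50 | above to above: no shift |
| 2.0 | 10.0 | 10/2 = 5.00 | above to above: no shift |
| 1.5 | 1.1 | 1.1/1.5 = 0.73 | above to above: no shift, although it fell |

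A 1.38-fold change counts as a shift and a 5.33-fold change does not. The first two rows share a cell, and that needs no assumption about raised baselines.

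**Step 2: how many patients could be affected.** There are 10 patients per arm (Section 4.1), so 20 on SPH3127. Let p be the proportion entering above ULN on a given test. The documents do not give p, so a range is assumed. The expected number is 20p, and the chance of at least one is 1 - (1 - p)^20.

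| Assumed p | Expected of 20 | Chance at least one enters above ULN |
|---|---|---|
| 2% | 0.4 | 1 - 0.98^20 = 33% |
| 5% | 1 | 1 - 0.95^20 = 64% |
| 10% | 2 | 1 - 0.90^20 = 88% |
| 20% | 4 | 1 - 0.80^20 = 99% |

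Each such patient is 1/20 = 5 percentage points of the pooled active group, or 1/10 = 10 points of one arm.

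**Step 3: chance that a rise is actually masked.** This also requires the patient to rise. Let r be the chance of a rise in a patient who enters above ULN, again assumed. The chance of at least one masked rise among 20 is 1 - (1 - rp)^20.

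| Assumed p | r = 10% | r = 30% |
|---|---|---|
| 2% | 1 - 0.998^20 = 4% | 1 - 0.994^20 = 11% |
| 5% | 1 - 0.995^20 = 10% | 1 - 0.985^20 = 26% |
| 10% | 1 - 0.99^20 = 18% | 1 - 0.97^20 = 46% |
| 20% | 1 - 0.98^20 = 33% | 1 - 0.94^20 = 71% |

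**Step 4: what the other displays add.**

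- By-visit statistics bear on size. A maximum, however, shows one value, without the number of patients who rose or their baselines.
- The Grade 2+ listing shows individual cases, with no stated count by arm and no stated link to baseline. The grade cut-offs are not in the documents, so which rises it would catch cannot be worked out here.
- Under Section 9.1, a pre-existing condition that worsens after dosing is an adverse event. Section 10.3.1 treats it as treatment-emergent and gives percentages by treatment group. Under Section 9.3, an abnormality the investigator judges not clinically significant is not reported.

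None of the three counts patients per arm by size of rise relative to baseline.

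**The case against.** The strongest reply is that the plan does not rest on the shift table alone. A worsening liver test that the investigator considers clinically significant enters the adverse event tables by arm, counted once per patient at maximum severity (Section 9.1). That route does not depend on visit timing, and a rise to 8 times ULN is unlikely to be dismissed. With 10 patients per arm, the Grade 2+ listing can be counted by hand. The study is exploratory and descriptive, and five ULN bands against baseline class will leave most cells at 0 or 1.

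Most of this stands, and it makes the point a modest one. It does not close the gap for smaller rises, where capture depends on judgment, and Section 1.3.1 describes the elevations as generally mild. The adverse event route also does not report size relative to baseline.

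A reader might infer four stronger things that the documents do not support.

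- *The arms cannot be compared on liver tests.* New elevations from normal remain countable if the shift tables are produced by arm, and by-visit statistics bear on size.
- *The table uses only an end-of-treatment reading.* Section 10.3.2 is silent, and by-visit tables are equally consistent with its wording.
- *Liver tests are the only laboratory signal.* Section 1.3.1 also reports neutropenia. Liver tests are the signal it describes as more frequent than on placebo.
- *The 64%, 88% and 99% figures are the chance of hiding a rise.* They are the chance, under assumed prevalences, that someone enters above ULN.

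**Conclusion.** The point holds as a limitation of one planned display. That display is the only one that shows laboratory change from baseline. It cannot show the size of a rise for any patient, and it tabulates a further rise in a patient entering above ULN as no shift. Both follow directly from the class definitions and exclusion 7. A missed transient rise is conditional: it occurs in this table only if the last value is the one used.

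The practical size rests on assumptions. At 5% to 20% entering above ULN, 1 to 4 of the 20 active patients are affected, and a rise is masked only in those who also rise. Other displays cover part of the gap. This is an inexpensive improvement worth making before the analysis. It is not a failure of the safety plan.

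**What to change.** Amend Section 10.3.2, or put the detail in an analysis plan, as follows.

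1. For ALT, AST, ALP, gamma-GT and total bilirubin, tabulate by arm the worst on-treatment value, from scheduled and unscheduled samples. Use multiples of ULN (up to 1, >1-2, >2-3, >3-5, >5) against the baseline class in the same bands.
2. For patients entering above ULN, also give the worst value as a multiple of their own baseline. State which pre-dose sample is baseline, since Section 7.6 has tests at both Screening and Day 1.
3. Report by arm the number of patients with ALT or AST >3 times ULN together with total bilirubin >2 times ULN. This is a descriptive count, not a rule for managing treatment.
4. For all other analytes, keep the normal-range shift tables, produce them by arm, and use the worst post-baseline value.

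The band limits are this review's choice; the documents do not set them. The cost is wording plus one or two descriptive tables from data already collected, with no new visits or samples. Cells will be sparse at 10 per arm, so the tables should be read alongside the Grade 2+ listing.

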10.3.3 Electrocardiogram (ECG)

The ECG variables that will be analyzed are heart rate, PR interval, QRS interval, QT interval, and corrected QT (QTc) interval using some or all of the following correction methods: QT corrected according to Bazett's formula (QTcB), QT corrected according to Fridericia's formula (QTcF).

Descriptive statistics of QTc intervals and changes from baseline will be summarized. The percentage of participants with QTc interval >450 milliseconds, >480 milliseconds, or >500 milliseconds will be summarized, as will the percentage of participants with QTc interval increases from baseline >30 milliseconds or >60 milliseconds.

10.3.4 Vital Signs

Descriptive statistics of temperature, pulse/heart rate, and blood pressure (systolic and diastolic) values and changes from baseline will be summarized at each scheduled time

point. The percentage of participants with values beyond clinically important limits will be reported.

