1.3.3 Efficacy and Pharmacodynamics in Humans

SPH3127 has a significantly longer pharmacodynamic than pharmacokinetic $t_{1/2}$ with significantly reduced plasma renin activity (PRA) with near complete inhibition within \sim 30 min of administration and full recovery at 48 hours with only the lowest doses. With repeated doses, PRA suppression is maintained at 70-90%.

As expected from its mechanism of action, SPH3127 produced reductions in both systolic and diastolic blood pressure in all clinical trials. Based on the results of a Phase 2a study in essential hypertension patients, a daily oral dose of 100 mg SPH3127 will be evaluated in future trials of its safety and effectiveness in essential hypertension. A dose of 50 mg QD or BID will be investigated for safety and efficacy in this trial (i.e., ulcerative colitis) to minimize the effects of SPH3127 on blood pressure and to evaluate the relative importance of dose and half-life on therapeutic activity.

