10 STATISTICS

10.1 General Procedures

Descriptive statistical methods will be used to summarize the data from this exploratory study, with the term descriptive statistics referring to the number of subjects (n), mean, median, standard deviation (SD), minimum, and maximum for continuous data and frequencies and percentages for categorical data. Analyses will be performed at both the end of the main 8-week study and the active treatment extension. All statistical testing will be 2-sided and performed using a significance (α) level of 0.05. Statistical comparisons to placebo will be to the individual and pooled doses of SPH3127. The

statistical analyses will be conducted with the SAS software package version 9.1.3 or higher (SAS Institute, Inc, Cary, North Carolina).

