10.3 Safety Analyses

The safety and tolerability of SPH3127 will be monitored by physical examinations, ECGs, clinical laboratory tests, vital signs, concomitant medications and AEs. Safety will be monitored through Day 63 (Main Study) or through the active treatment extension period, if applicable.

All treatment-emergent AEs will be summarized by treatment group and Medical Dictionary for Regulatory Activities (MedDRA) system organ class and preferred terms for each group of participants.

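### Blood-pressure falls from baseline are displayed by time point but never counted per patient, and the limits for the one patient-level count have no number

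*Combined protocol and SAP*

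**What the plan says.** Section 10.3.4 states that "blood pressure (systolic and diastolic) values and changes from baseline will be summarized at each scheduled time" point. Section 10.1 defines descriptive statistics as the number of subjects plus "mean, median, standard deviation (SD), minimum, and maximum for continuous data". The minimum change, which is the largest individual fall at that time point, is therefore part of the planned output.

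The only patient-level rule for blood pressure is in the same section: "The percentage of participants with values beyond clinically important limits will be reported". No numeric limit is given. The one numeric blood-pressure limit in the protocol is exclusion criterion 16 in section 5.4 (systolic below 90 or diastolic below 60 mmHg at screening), which is an entry rule and not an analysis limit.

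For QTc, section 10.3.3 counts patients above 450, 480 and 500 ms and also "the percentage of participants with QTc interval increases from baseline >30 milliseconds or >60 milliseconds".

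Section 1.3.3 reports that "SPH3127 produced reductions in both systolic and diastolic blood pressure in all clinical trials". Sections 1.3.1 and 1.3.3 give limiting the effect on blood pressure as a reason for the doses chosen, and section 2.1 makes safety and tolerability the primary objective. Sections 6.2.2, 6.2.4 and 6.2.5 collect blood pressure before dosing and at 30 minutes, 2, 4 and 8 hours after dosing on Days 1, 28 and 56. Section 4.1 allows baseline to be taken at screening or on Day 1 before treatment.

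**The concern.** A trial that chose its doses partly to limit blood-pressure effects should be able to say how many patients on each arm had a material fall. The planned output does not give that number. A count of values beyond a limit depends on where the patient started: with a limit of 90 mmHg, a fall from 140 to 95 is not counted. A summary at each time point shows the size of the largest change but does not link time points within a patient. Three large falls at three times could be three patients out of 10 or one patient three times.

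At stake is whether the main-study report can give a proportion of patients with falls on SPH3127 to set beside placebo. The serial readings already collected would allow this, and the plan does the equivalent for QTc.

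**Working it through.** The plan states no blood-pressure threshold, variance or expected effect, so there is no figure to reproduce. The steps below use the plan's structure and, where marked, assumed inputs.

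**1. Time points.** After the first dose in the main study there are 4 on Day 1, 1 on Day 14, and 5 each on Days 28 and 56 (one pre-dose, four post-dose): 4 + 1 + 5 + 5 = 15. Each has its own minimum. Nothing in section 10.3.4 joins them within a patient.

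**2. What the planned output shows for one fall (assumed data).** In an arm of 10, one patient goes from 145 to 105 and nine do not change. Change from baseline: mean −40/10 = −4.0, median 0, SD 12.6, minimum −40. Patients below an assumed limit of 90: 0 of 10. The minimum shows the fall, the value count does not, and a change count would read 1 of 10.

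**3. Dependence on starting value.** With an assumed limit of 90, a fall of size f crosses it only from a baseline below 90 + f, that is below 110, 120 or 130 for falls of 20, 30 or 40 mmHg. For a single fall without reading error, the share not counted is P(baseline ≥ 90 + f) / P(baseline ≥ 90). Over assumed normal baselines with mean 120 to 130 and SD 10 to 15:

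| Fall (mmHg) | Share not counted |
|---|---|
| 20 | 76 to 98% |
| 30 | 50 to 84% |
| 40 | 16 to 50% |

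**4. Simulation with serial readings.** Assumed inputs: usual systolic pressure mean 122, SD 13, cut at 95; reading SD 6 or 8; 30% of an active arm affected; one 30 mmHg fall per intensive sampling day at a random one of four post-dose times; 12 post-dose readings; change taken from the Day 1 pre-dose value.

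| | Reading SD 6 | Reading SD 8 |
|---|---|---|
| Affected patients flagged, any value < 90 | 58% | 62% |
| Affected patients flagged, any fall ≥ 30 | 75% | 75% |
| Unaffected patients flagged, any value < 90 | 3.2% | 6.7% |
| Unaffected patients flagged, any fall ≥ 30 | 0.2% | 3.4% |

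For 35 mmHg falls the two rules flag 72 to 75% and 88 to 91% of affected patients.

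Expected counts in an arm of 10 with three affected patients:

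- Change rule: 3 × 0.75 + 7 × 0.002 = 2.26 (SD 6) and 3 × 0.75 + 7 × 0.034 = 2.49 (SD 8), against 0.02 and 0.34 in a no-effect arm.
- Value rule: 3 × 0.58 + 7 × 0.032 = 1.96 and 3 × 0.62 + 7 × 0.067 = 2.33, against 0.32 and 0.67.

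**5. What the minima show in the same scenario.** At least one time-point minimum of −30 or worse appears in about 92 to 94% of active arms. In no-effect arms it appears with probability 1 − (1 − 0.002)^10 = 2% at SD 6 and 1 − (1 − 0.034)^10 = 29% at SD 8. With no drug effect at all, the deepest of the 12 post-dose minima averages −20 (SD 6) or −27 (SD 8).

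**6. The mean.** If falls come at random times, the mean change at each post-dose time is −0.30 × 30 / 4 = −2.25 mmHg. If they share one scheduled time, it is −0.30 × 30 = −9 mmHg there.

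**The case against.** A reader might infer that blood pressure is analysed only through means, so that a large fall is averaged away and the trial could report little effect. The documents do not support that. Section 10.1 puts the minimum and maximum in every descriptive summary and section 10.3.4 applies this to changes from baseline, so the largest fall at each time point is displayed by arm. Step 5 shows that it would usually be visible. The small mean of about −2 mmHg rests on random timing. Section 1.3.2 puts peak concentration at about 30 to 60 minutes and section 1.3.3 reports near-complete inhibition of renin activity within about 30 minutes, so falls may well cluster in time. The timing of the blood-pressure effect itself is not given.

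Two further inferences go beyond the text. Section 10.3.4 does not call its limits absolute or set them at 90 mmHg; that figure is borrowed here for illustration, and another limit would change the capture rates. Nor do the documents name blood-pressure reduction as the main harm: section 1.3.1 calls it known pharmacology and also reports liver-test elevations more often than on placebo.

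Adverse events are a second patient-level route. Section 10.3.1 counts patients with at least one occurrence of each event, so reported hypotension and dizziness are each counted. Section 1.3.1 links the two ("Dizziness, likely as a consequence of hypotension, occurred only at the higher doses of SPH3127"), but a pooled adverse-event row would be a reporting preference and this point does not rest on it. A fall without symptoms may not be recorded as an event, so this route does not replace a count of measured falls.

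Finally, the study is exploratory, has no power calculation, and could add tables later. That lowers the weight of the point. But change categories chosen after unblinding would be less credible than ones fixed in advance.

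**Conclusion.** The gap is real but limited. The plan displays changes in blood pressure, including the largest at each time point. It does not count patients with a given fall, does not give each patient's largest fall, and puts no number on the limits that it does count against. Separate minima over 15 time points cannot supply the missing proportion, and with noisy readings they can look large without any drug effect.

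Under the assumed inputs, a change criterion flags about 75% of patients with 30 mmHg falls against 58 to 62% for the value limit, with fewer false flags. That is a useful gain, not a rescue: the value limit still catches more than half. The size depends on the assumed baseline distribution, reading error, borrowed limit, and a change cut-off set equal to the assumed fall. Diastolic pressure was not modelled. Counts in arms of 10 will remain imprecise: at a true rate of 10%, the chance of seeing at least one such patient is 1 − 0.9^10 = 65% in one arm and 1 − 0.9^20 = 88% in the 20 pooled active patients.

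**What to change.** In section 10.3.4 add, from readings already collected:

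1. Each patient's largest post-dose fall in systolic and diastolic pressure from the Day 1 pre-dose value, on Days 1, 28 and 56, summarised by arm and for pooled SPH3127 against placebo. Naming the Day 1 pre-dose value also settles, for this analysis, the choice of baseline that section 4.1 leaves open.
2. The number and percentage of patients with falls beyond change categories that the sponsor fixes before unblinding, placed next to the value limits, as section 10.3.3 does for QTc. The numbers behind the value limits should be written down at the same time.

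The cost is a few lines of analysis text and two or three more safety tables, with no new data. The downside is that the worst of several readings shows apparent falls in every arm, placebo included, so the tables must be read against placebo and not on their own. This is a change to the analysis only. It sets no clinical threshold and no management rule.
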